3.2.4. Incidence of the development of antidrug antibody (ADA) and neutralizing antibody (NAb)

Blood samples (approximately 5 mL) to provide at least 2 mL of serum to detect ADA and NAb against PF 06730512 (~1 mL each of ADA and Nab) will be collected from subjects enrolled at the times specified in the Schedule of Activities.

CCI

CCI

CCI

3.4. Safety Endpoints

3.4.1. Adverse Events (AEs)

An adverse event is considered treatment emergent relative to a given treatment if:

- the event occurs for the first time during the Investigational Treatment Period and was not seen prior to the start of treatment (during the Lead-in Period), or
- the event was seen prior to the start of treatment but increased in severity during treatment.

Adverse events occurring during the Lead-in Period are considered non-treatment emergent. Events that occur during the Follow-Up Period will be counted as treatment emergent and attributed to the previous treatment taken.

A 3-tier approach for summarizing AEs will not be used for this study as a placebo or active comparator arm is not included in the design and there is a low number of subjects planned to be enrolled.

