Safety monitoring will commence once the subject has provided informed consent. In the Lead-in Period, the focus will be on possible symptoms and complications of nephrotic syndrome including edema in peripheral (facial, extremity) and central (pleural effusion, ascites) locations, weight gain due to edema, ulcerations and infections in edema-dependent regions and worsening of hypertension. In addition, adverse events may occur due to thromboembolic complications related to FSGS which may manifest as renal venous thrombosis potentially extending to the inferior vena cava, deep venous thrombosis of the lower extremities and subsequent pulmonary embolism.⁷ Adverse events may be related to side effects of previous or current FSGS therapy including cataracts, osteoporotic bone disease or avascular necrosis of the femoral head. A prolonged course of corticosteroids is associated with significant side effects, including diabetes, increased infection rates, osteoporosis, and weight gain. Nephrotoxicity is of great concern in the usage of calcineurin inhibitors in treatment of steroid-resistant FSGS with chronically impaired renal function.

[REDACTED]

CCI

[REDACTED]

[REDACTED]

[REDACTED]

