8.1.4. Time Period for Collecting AE/SAE Information

The time period for actively eliciting and collecting AEs and SAEs (“active collection period”) for each subject begins from the time the subject provides informed consent, which is obtained before the subject’s participation in the study (ie, before undergoing any study-related procedure and/or receiving investigational product), through and including a minimum of 70 ± 7 calendar days after the last administration of the investigational product.

For subjects who are screen failures, the active collection period ends when screen failure status is determined.

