8.3. Severity Assessment

If required on the AE page of the CRF, the investigator will use the adjectives MILD, MODERATE, or SEVERE to describe the maximum intensity of the AE. For purposes of consistency, these intensity grades are defined as follows:

MILD	Does not interfere with subject's usual function.
MODERATE	Interferes to some extent with subject's usual function.
SEVERE	Interferes significantly with subject's usual function.

Note the distinction between the severity and the seriousness of an AE. A severe event is not necessarily an SAE. For example, a headache may be severe (interferes significantly with the subject's usual function) but would not be classified as serious unless it met one of the criteria for SAEs, listed above.

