6.6.1. Adverse Events

Listings and summary tables of adverse events will be based on the SAS.

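### Read at the term level, the SAP's treatment-emergent rule drops on-treatment recurrences of Lead-in events unless severity rises, yet counts every Follow-up event without that test

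*SAP*

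**What the plan says.** SAP 3.4.1 gives two routes by which an on-treatment event becomes treatment emergent:

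- New event: "the event occurs for the first time during the Investigational Treatment Period and was not seen prior to the start of treatment". A parenthesis that follows ties the prior sighting to the Lead-in Period.
- Worsened event: "the event was seen prior to the start of treatment but increased in severity during treatment".

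Two sentences deal with the other periods: "Adverse events occurring during the Lead-in Period are considered non-treatment emergent", and "Events that occur during the Follow-Up Period will be counted as treatment emergent and attributed to the previous treatment taken".

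The SAP makes no exception for a resolved event that recurs, or for one that becomes serious. It does not say whether an event is matched by coded term or by episode. On outputs, SAP 6.6.1 says only: "Listings and summary tables of adverse events will be based on the SAS".

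In the protocol, AE collection "begins from the time the subject provides informed consent" (8.1.4), so every treated subject has a pre-dose AE record. Section 8.3 grades severity as mild, moderate or severe and notes that "A severe event is not necessarily an SAE". Section 1.3.1 explains that there is no placebo and that safety will be judged by comparing the Lead-in with the Treatment Period and with historical data. It lists edema and, among other nephrotic complications, "ulcerations and infections in edema-dependent regions and worsening of hypertension" as the focus of Lead-in safety monitoring.

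**The concern.** Take a subject with moderate cellulitis in the Lead-in that resolves, and a new moderate cellulitis at Week 9 that leads to admission. At the term level this is not a first occurrence and its severity has not risen, so neither route applies, although it is a serious event on treatment. If the Lead-in episode was graded severe, no recurrence in the Treatment Period can qualify, because the scale has no higher grade. Had the same recurrence come at Week 27, the Follow-up sentence would count it.

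Safety and tolerability is a secondary objective and there is no control arm. The Lead-in versus Treatment comparison needs the same counting on both sides. Here a Lead-in event is an event whenever it occurs, but an on-treatment event of the same kind carries the flag only if it is new or worse. The comparison tilts towards the drug for recurring conditions, which are what the protocol tells sites to watch for.

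**Working it through.** **The rule, case by case (term-level reading)**

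| Period of event | Seen in Lead-in? | More severe? | Treatment emergent? |
|---|---|---|---|
| Treatment | no | n/a | yes |
| Treatment | yes | yes | yes |
| Treatment | yes | no | **no** |
| Follow-up | no | n/a | yes |
| Follow-up | yes | yes | yes |
| Follow-up | yes | no | **yes** |

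The third and last rows are the same recurrence with opposite outcomes. Seriousness appears nowhere in the rule.

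**Illustrative size**

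The documents give no event rates and no figure to reproduce.

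Inputs from the documents: Lead-in about 8 weeks, treatment up to 24 weeks, visits in Follow-up from Week 25 to Week 33 (taken as 8 weeks), up to about 22 subjects per cohort (Protocol Summary, 3.1 and 6.3).

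Assumptions: an event type seen in 20% of subjects in the Lead-in, constant rate, no drug effect, unchanged severity.

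Let P(k) be the probability of no event in k units of 8 weeks.

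- Equal risk: P(k) = 0.8^k.
- Gamma frailty with variance v: P(k) = (1 + v·k·m)^(−1/v), with m set so that P(1) = 0.8. The values v = 1 and v = 2 are assumptions.

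| | P(1) | P(2) | P(3) | P(4) | P(5) |
|---|---|---|---|---|---|
| Equal risk | 0.800 | 0.640 | 0.512 | 0.410 | 0.328 |
| v = 1 | 0.800 | 0.667 | 0.571 | 0.500 | 0.444 |
| v = 2 | 0.800 | 0.686 | 0.610 | 0.555 | 0.512 |

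*On-treatment-only table.* Affected = 1 − P(3). Flagged = P(1) − P(4), that is, no Lead-in event but at least one on treatment.

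- Equal risk: 48.8% affected, 39.0% flagged; lost 9.8/48.8 = 20%. In 22 subjects: 10.7 affected, 2.2 lost.
- v = 1: 42.9% affected, 30.0% flagged; lost 12.9/42.9 = 30%.
- v = 2: 39.0% affected, 24.5% flagged; lost 14.5/39.0 = 37%.

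*Subject-level table that includes Follow-up.* A subject is lost only with an event in the Lead-in, an event on treatment, and none in Follow-up: P(1) − P(2) − P(4) + P(5). Affected after first dose = 1 − P(4).

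- Equal risk: 7.8% of 59.0% = 13%; 22 × 0.078 = 1.7 subjects.
- v = 1: 7.8% of 50.0% = 16%; 1.7 subjects.
- v = 2: 7.1% of 44.5% = 16%; 1.6 subjects.

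*Sensitivity.* In the on-treatment-only table, the loss is 10-22% of affected subjects at 10% Lead-in incidence and 30-49% at 30%. SAP 2.2 gives 12 weeks of treatment to subjects enrolled before Amendment 5. For them, under equal risk and 20% incidence, 22 × (1 − 0.8^1.5) = 6.3 subjects are affected and 20% of these, about 1.3, are lost. The number is smaller; the share in that table is the same.

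**The case against.** Several counter-arguments have weight.

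- **Deliberate screen.** Protocol 1.3.1 says the Lead-in should help separate the course of FSGS from drug effects, and discounting same-severity events seen before dosing fits that aim. This stands as a motive. It does not explain why the screen stops at Follow-up, or why a new or newly serious episode is treated as background.
- **Event may mean episode.** Protocol 8.2.1 defines an AE as an occurrence. If each new episode is a new event, the cellulitis example qualifies and most of the loss goes. The first-time, not-seen-before wording leans towards the term, but the SAP does not settle it.
- **Residual exposure.** Week 27 (Day 183) is 28 days after the last dose (Day 155). With the mean half-lives of 5.3 to 13 days in Protocol 1.2.5.2, that is roughly 2 to 5 half-lives, so attributing Follow-up events to treatment is reasonable. It justifies counting them, not a looser test than the one applied during dosing.
- **Other safeguards.** Blood pressure and body weight are summarised as change from baseline (SAP 6.6.3, 6.6.5), and discontinuations due to AEs are reported separately (SAP 6.5.4).

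A reader might infer that on-drug SAEs vanish from the study's reporting, or that the reported SAE incidence is lowered. The documents do not support that. SAEs and non-serious AEs are recorded on the CRF, and SAEs are reported to the sponsor, whatever their emergence status (Protocol 8.1.4.1, 8.1.4.2). SAP 6.6.1 does not tie any SAE table to the flag. Nor does the rule remove all disease-related events: first occurrences on treatment and worsened events still count.

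**Conclusion.** The defect is in the definition. On the term-level reading, SAP 3.4.1 withholds the flag from same-severity on-treatment recurrences of Lead-in events and gives it to the same recurrences in Follow-up. Any table using the flag understates on-treatment incidence relative to the Lead-in, in a trial whose safety assessment leans on that comparison.

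The size is illustrative and rests on assumed rates. The 20-37% range applies only to an on-treatment-only table, which the SAP does not specify; the 13-16% range applies if Follow-up is included. Both shrink if some recurrences are more severe. A reader might add the Screening Period of up to 43 days as further time for events to be seen first, but the Lead-in parenthesis leaves Screening-only events unclear, so the argument rests on the Lead-in alone.

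This should be corrected. It is a flaw in classification and tabulation, not a loss of safety data.

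**What to change.** In SAP 3.4.1, replace the two bullets and the Follow-up sentence with one rule for both the Treatment and Follow-up Periods. An AE is treatment emergent if either:

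- its onset is on or after the first dose, including a new episode of an event that resolved before dosing; or
- it was ongoing at first dose and then worsened in severity or became serious.

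State the matching level (for example, preferred term), flag each event whose preferred term also occurred before dosing, and say in SAP 6.6.1 which AE and SAE tables use the treatment-emergent flag.

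If the sponsor's definition must stay, add one table of all AEs and SAEs with onset on or after first dose, carrying the pre-dose flag. That keeps the screen for background disease and shows what it removes.

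The cost is SAP wording, one derived flag and at most one table. Onset dates and severity are already collected, and the present rule needs both. The downside is somewhat higher treatment-emergent percentages that include background disease, which the pre-dose flag identifies.

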3.4.2. Laboratory Data

Safety laboratory tests (hematological, clinical chemistry (serum), urinalysis and other safety tests) will be performed as described in the protocol.

To determine if there are any clinically significant laboratory abnormalities, the hematological, clinical chemistry (serum) and urinalysis safety tests will be assessed against the criteria specified in the sponsor reporting standards. The assessment will take into account whether each subject's baseline test result is within or outside the laboratory reference range for the particular laboratory parameter.

Baseline for all laboratory measurements will be defined as the pre-dose Day 1 (Week 1) measurement.

3.4.3. Vital Signs

Vital sign measurements (sitting blood pressure, pulse rate, and oral body temperature) will be taken as detailed in the Schedule of Activities given in the protocol.

Baseline is defined as the pre-dose Day 1 (Week 1) measurement. Changes from baseline for sitting systolic and diastolic blood pressure, pulse rate and body temperature will be

calculated for each post baseline measurement, as that measurement minus the baseline value.

3.4.4. Electrocardiogram (ECG)

A single standard 12-lead ECG (including QT, QTc, PR, QRS and heart rate) will be obtained at times detailed in the Schedule of Activities given in the protocol.

Baseline will be defined as the pre-dose Day 1 (Week 1) measurement. Change from baseline will be calculated for each post baseline measurement, as that measurement minus the baseline value.

3.4.5. Body Weight

Body Weight will be measured at times detailed in the Schedule of Activities given in the protocol.

Baseline will be defined as the pre-dose Day 1 (Week 1) measurement. Change from baseline will be calculated for each post baseline measurement, as that measurement minus the baseline value.

4. ANALYSIS SETS

4.1. Full Analysis Set

The Full Analysis Set (FAS) is defined as all enrolled subjects who have received at least one dose of study treatment and have at least one post-baseline measurement of UPCR based on 24-hour urine collection.

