9.2.1. Analysis of the Primary Endpoint

The primary analysis will be based on the full analysis set (FAS), which will be defined to be all enrolled subjects who have received at least one dose of study treatment and have at least one post-baseline measurement of UPCR. A mixed effects model of repeated measures (MMRM) will be fitted to the post-dose 24-urine collection data on UPCR (ie, Weeks 5, 9 and 13) using data through Week 13. The model will include treatment (if more than one dose), baseline, week (as a factor), baseline*week interaction and the week*treatment (if more than one dose) interaction, with week fitted as a repeated effect, and subject as a random effect. An unstructured correlation matrix will be used to estimate the variances and covariance within subject across time points. If convergence is not obtained or model fit is not adequate, then other covariance structures will be investigated as necessary. The Kenward-Roger approximation will be used for estimating degrees of freedom for the model parameters. The percentage change from baseline to Week 13 treatment effect(s) will be the primary comparison(s) of interest.

The probabilities for the decision criteria for each of the doses (as required) will be calculated using the results of the MMRM.

The back-transformed Least Squares Means (LSMeans) together with 90% confidence intervals will be obtained for each dose (if applicable) and week.

Ratios in LSMeans (calculated by back-transforming modelled results), amongst the doses at the different weeks, together with 90% confidence intervals, will also be obtained if applicable.

All values for UPCR (including baseline) will be \log_e -transformed prior to analyses, where analysis of changes from baseline will be performed. The percentage change from baseline will be derived by transforming the ratio using the following formula:

$$\text{Percentage change from baseline} = 100 * ([\text{back-transformed LSMean}] - 1)$$

Plots will be produced including:

- The treatment back-transformed LSMeans (including confidence intervals) for each dose (as required) over time.

Missing values will be imputed as part of the MMRM model assumptions.

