3.2. Secondary Endpoint(s)

3.2.1. Percentage change from baseline to Weeks 2, 5, 9, and beyond Week 13, as applicable, in Urinary Protein to Creatinine Ratio (UPCR)

The secondary efficacy endpoints include percentage change from baseline to Weeks 2, 5 and 9 in UPCR based on both the 24-hour urine collections and the first morning voids. All analyses and descriptive summaries will report first morning void assessments and 24-hour urine assessments of UPCR separately. Descriptive statistics will be used to summarize UPCR by dose and timepoint for all timepoints in the Lead-in Period and the Investigational Treatment Period, as well as Week 13 data for subjects enrolled prior to amendment 5 and Week 25 data for subjects enrolled after amendment 5.

For descriptive summaries, percentage change from baseline will be calculated for each post-baseline measurement based on the respective urine collection, as that measurement minus the baseline value divided by the baseline value multiplied by 100.

3.2.2. Percentage change from baseline to Weeks 3, 5, 9, 13 and beyond, as applicable, in estimated glomerular filtration rate (eGFR)

The secondary efficacy endpoints of percentage change from baseline in estimated glomerular filtration rate (eGFR) include Weeks 3, 5, 9 and 13. Descriptive statistics will be used to summarize eGFR by dose and timepoint for all timepoints in the Lead-in Period and the Investigational Treatment Period, as well as Week 13 data for subjects enrolled prior to amendment 5 and Week 25 data for subjects enrolled after amendment 5.

The eGFR will be calculated based on the Chronic Kidney Disease Epidemiology Collaboration (CKD-EPI) formula¹ (see Appendix 4).

Baseline is defined as the Week -1 measurement. If the Week -1 eGFR measurement is not available, the nearest eGFR measurement taken to the Week -1 visit will be used, provided it is pre-dose.

Log-transformed change from baseline will be the dependent variable in the analysis models. The percentage change from baseline will be calculated for each post-baseline measurement, as that measurement minus the baseline value divided by the baseline value multiplied by 100.

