5.3.3. Mixed Model Repeated Measures (MMRM)

The efficacy analyses over time will be based on the FAS and will use a mixed model repeated measures (MMRM) approach. The mixed effect repeated measures model will include baseline, week (as a factor), baseline*week interaction, and will use an unstructured covariance matrix for within-subject time-dependent correlation.

If convergence is not obtained or model fit is not adequate then other covariance structures will be investigated as necessary. The Kenward-Roger approximation will be used for estimating degrees of freedom for the model parameters.

The probabilities for the decision criteria (listed in Section 5.2) for each of the doses (as required) will be calculated using the results of the MMRM (e.g. back-transformed LSmean estimate, standard error and degrees of freedom for Week 13).

[figure not shown]
[figure not shown]
[figure not shown]
The Least Squares Means (LSMeans) (back-transformed if log_e transformation is performed) together with 90% confidence intervals and standard errors will be obtained for each dose individually (if applicable) and week, and will be summarized in a table and a profile plot with a separate plot for each dose (if applicable).

Ratios in LSMeans (calculated by back-transforming modelled results if \log_e transformation is performed), between doses at the different weeks, together with 90% confidence intervals and standard errors, will also be obtained if applicable.

CCI

CCI

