6.2. Secondary Endpoint(s)

6.2.1. Percentage change from baseline to Weeks 2, 5, 9, and beyond Week 13, as applicable, in Urinary Protein to Creatinine Ratio (UPCR)

The analysis methodology for this secondary endpoint is summarized in Section 3.2.1.

For the CSR, an additional summary statistic table will be provided that is based on the respective SAS population.

6.2.2. Percentage change from baseline to Weeks 3, 5, 9, 13 and beyond, as applicable, in estimated glomerular filtration rate (eGFR)

The analysis for this eGFR endpoint will follow the same type of MMRM model and descriptive summary statistics as the primary analysis model (Section 6.1.1). Additional details regarding the handling of the eGFR endpoint can be found in Section 3.2.2.

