SS	eGFR	FAS	Statistical Summary of MMRM Analysis of estimated Glomerular Filtration Rate (eGFR) - FAS	13	14.2.2.1.2 in IA2 & IA3
P	eGFR	FAS	Individual Subject Data Plot of estimated Glomerular Filtration Rate (eGFR) - FAS	14	Figure 14.2.2.1.3, Figure 14.2.2.1.4 in IA2 & IA3
P	eGFR	FAS	LS Mean profile (including 90% CI) plot for estimated Glomerular Filtration Rate (eGFR) - FAS	15	Figure 14.2.2.1.5 in IA2 & IA3

[figure not shown]

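### The eGFR outputs are restricted to subjects with a post-baseline 24-hour UPCR, so a dosed subject with post-dose eGFR but no usable 24-hour urine is left out of them

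*SAP*

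**What the plan says.** - **Entry to the FAS.** SAP 4.1 requires at least one dose and that the subject "have at least one post-baseline measurement of UPCR based on 24-hour urine collection". Protocol 9.2.1 is wider. It asks that subjects "have received at least one dose of study treatment and have at least one post-baseline measurement of UPCR", without naming the type of collection, and it does so in the section on the primary analysis.
- **Use of the FAS.** SAP 5.3.3: "The efficacy analyses over time will be based on the FAS and will use a mixed model repeated measures (MMRM) approach".
- **Status of eGFR.** SAP 3.2.2: "The secondary efficacy endpoints of percentage change from baseline in estimated glomerular filtration rate (eGFR) include Weeks 3, 5, 9 and 13". SAP 6.2.2: "The analysis for this eGFR endpoint will follow the same type of MMRM model and descriptive summary statistics as the primary analysis model".
- **Outputs.** Appendix 1.1 assigns the FAS to the eGFR listing, summary, model, individual plot and LS-mean plot (outputs 11 to 15). The model row, for example, reads "Statistical Summary of MMRM Analysis of estimated Glomerular Filtration Rate (eGFR) - FAS". The same appendix repeats FAS outputs for first-morning-void UPCR.
- **Safety Analysis Set.** For UPCR, SAP 6.2.1 says that "an additional summary statistic table will be provided that is based on the respective SAS population". SAP 6.2.2 has no counterpart for eGFR.
- **Per-protocol set.** SAP 4.2 makes it a subset of the FAS, so it cannot bring anyone back.

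**The concern.** For the 24-hour UPCR analysis the entry condition is harmless: a subject with no post-baseline 24-hour UPCR contributes nothing to that model anyway. For eGFR it is a condition on a different specimen. eGFR comes from blood drawn at the site, whereas 24-hour urine is collected at home, can be incomplete, and is due at fewer visits. Applied literally, the plan discards observed post-dose eGFR on a stated secondary objective, the effect on renal function.

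If the excluded subjects had left with declining renal function, the reported eGFR change would look better than the change in all dosed subjects with data. The SAP's version history mentions emerging discontinuations, so early leaving is not hypothetical. The first-morning-void repeats have the same problem in milder form: a subject can have the relevant specimen and still be outside the set.

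**Working it through.** The plan states no figure that depends on this set, so the check is mainly one of logic. The arithmetic only gives scale.

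**Step 1. Which eGFR outputs use the FAS?** Five of the five eGFR rows in Appendix 1.1 do. These rows are not redacted. No eGFR-specific set is defined in SAP section 4.

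**Step 2. Who has post-dose eGFR but fails the FAS condition?** One usable 24-hour UPCR at any post-baseline visit is enough for entry.

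| | First scheduled post-dose eGFR | First scheduled post-dose 24-hour urine |
|---|---|---|
| After Amendment 5 (Protocol 6.2) | Week 3 | Week 2 |
| Before Amendment 5 (inferred) | Week 3 | Week 5 |

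The second row is inferred. The amendment history says that urine sampling was added at Week 2, and the primary model uses Weeks 5, 9 and 13. The earlier protocol is not among the documents, and the Week 3 eGFR is assumed to have been in it. SAP 2.2 confirms that some analysed subjects enrolled before Amendment 5.

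- Before Amendment 5, the main case is a subject who left between Weeks 3 and 5 without an early-termination urine.
- After Amendment 5, it is a subject with no usable collection at Week 2 or at any later visit.

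**Step 3. Scale.** Let k be the number excluded from a cohort of 22 (the Protocol Summary gives up to approximately 22). The documents do not give k, so 1 to 4 is assumed. The upper value is 22 − 18, using the approximately 18 subjects in Protocol 9.6, and is meant only as an outer limit.

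- Share of the cohort, k/22: 1/22 = 4.5%, 2/22 = 9.1%, 4/22 = 18.2%.
- Inflation of the standard error from the lost subjects, √(22/(22 − k)): √(22/21) = 1.02, √(22/20) = 1.05, √(22/18) = 1.11.

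**Step 4. Possible shift in the mean at a visit where the excluded subjects have data.** Assume that retained subjects change by −3% and excluded subjects by m. The mean with all of them included, on the log scale, is

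100 × (exp{[(22 − k) ln 0.97 + k ln(1 + m)]/22} − 1).

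For k = 1 and m = −20%: (21 × −0.0305 − 0.2231)/22 = −0.0392, or −3.8%. Over the assumed range:

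| m | k = 1 | k = 2 | k = 4 |
|---|---|---|---|
| −10% | −3.3% | −3.7% | −4.3% |
| −20% | −3.8% | −4.7% | −6.3% |
| −30% | −4.4% | −5.8% | −8.6% |

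The FAS result would be −3.0% in every cell.

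**Step 5. Week 13 model estimate.** A subject with only a Week 3 value reaches Week 13 through the within-subject correlation. If b is the slope of Week 13 on Week 3, and retained subjects are at −3% at both visits, the log estimate is approximately ln 0.97 + b(k/22)[ln(1 + m) − ln 0.97]. For k = 1 and m = −20%, the bracket is −0.2231 + 0.0305 = −0.1927, and −0.1927/22 = −0.0088. Then b = 0 gives −3.0%, b = 0.5 gives exp(−0.0305 − 0.0044) − 1 = −3.4%, and b = 1 gives −3.8%. The Step 4 figures are therefore an upper limit for Week 13 when b is between 0 and 1.

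**The case against.** The strongest reply is that the gap is narrow and partly covered elsewhere.

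- **Few subjects qualify.** A reader might infer that anyone leaving at a visit with blood but no 24-hour urine is dropped. That is not so: a subject leaving at Week 7, 11 or 15 normally already has a usable collection and stays in the FAS. The protocol also asks withdrawing subjects to attend an early-termination visit, at which a 24-hour urine is expected (Schedule of Activities, footnotes i and o). Subjects who stop treatment remain in follow-up (6.4), and repeat collections and a separately shipped reserve aliquot are allowed (7.2.1). This stands, and it makes the affected group probably small.
- **Bias is not shown.** A reader might infer that the eGFR result is biased in the drug's favour. The documents do not say why subjects leave, nor that those without urine had falling eGFR. This stands.
- **Renal worsening is still visible.** Creatinine is in the chemistry panel, and laboratory and adverse-event summaries use the Safety Analysis Set (SAP 6.6). This stands in part. Those summaries use a Day 1 baseline (SAP 3.4.2), whereas eGFR uses Week −1 (SAP 3.2.2), and they do not give the eGFR percentage change.
- **Appendix 1.1 may be incomplete.** The UPCR table promised in SAP 6.2.1 is not among its visible rows, and parts of the SAP are redacted. The claim is therefore limited to the visible outputs.
- **The study is well advanced.** FAS-based eGFR outputs were specified for IA2 and IA3, which SAP 7.1 describes as done. Changing the set now is a data-aware change. This bears on how to make the fix, not on whether the restriction is sound.

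**Conclusion.** The point holds as a limited one. The FAS condition has no purpose for eGFR, yet it governs all five visible eGFR outputs and the first-morning-void repeats, and no Safety Analysis Set table fills the gap as one does for UPCR. Followed exactly, the plan omits observed post-dose eGFR for any dosed subject without a usable post-baseline 24-hour urine.

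The number affected is unknown and probably small; each such subject is 4.5% of a cohort of 22. The exclusion may bias the eGFR result if such subjects left with worsening renal function, but size and direction are unknown. The figures in the working rest on assumed k, m and b and are not estimates for this trial. The pre-Amendment 5 case also rests on an inferred schedule.

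The primary endpoint is not affected, and neither are the decision criteria in SAP 5.2, which concern proteinuria reduction and are computed from the Week 13 UPCR model.

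**What to change.** In SAP 4.1, 6.2.2 and Appendix 1.1:

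1. Base the eGFR listing, summary, model and plots on all dosed subjects with a baseline and at least one post-baseline eGFR.
2. Use the analogous rule for first-morning-void UPCR: a baseline and at least one post-baseline value from that collection.
3. Keep the FAS, with its 24-hour UPCR condition, for the primary endpoint.
4. Because FAS-based eGFR outputs were already specified for IA2 and IA3, keep the FAS version alongside for comparison, and record the change as made after those analyses.
5. Report how many dosed subjects have post-dose eGFR but fall outside the FAS, so that the reader can see whether the choice matters.

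At minimum, add an eGFR summary and listing on the Safety Analysis Set, following what SAP 6.2.1 already does for UPCR with a summary table.

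The cost is SAP wording, a population flag and a few extra outputs, with no new data. N may differ slightly between endpoints and should be shown on each table.
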